## 12.2 Appendix B - GAI Scale

Table 1 - Global Aesthetic Improvement (GAI) scale to be used for both investigator and subject evaluation:

(3)	Very Much Improved
(2)	Much Improved
(1)	Improved
(0)	No Change
(-1)	Worse
(-2)	Much Worse
(-3)	Very Much Worse

Confidential 22

## 12.3 Appendix C - Photographs Assessment Log

## Independent Evaluators' Form

Subject	ID	Treated Area	Slide Set #	GAI score
(initials)				
		☐Mons Pubis ☐Labia	$\square$ Baseline + $\square$ FU1/ $\square$ FU2/ $\square$ FU3	
		☐Mons Pubis ☐Labia	$\square$ Baseline + $\square$ FU1/ $\square$ FU2/ $\square$ FU3	
		☐Mons Pubis ☐Labia	$\square$ Baseline + $\square$ FU1/ $\square$ FU2/ $\square$ FU3	
		☐Mons Pubis ☐Labia	$\square$ Baseline + $\square$ FU1/ $\square$ FU2/ $\square$ FU3	
		☐Mons Pubis ☐Labia	☐Baseline + ☐FU1/☐ FU2/ ☐FU3	
		☐Mons Pubis ☐Labia	☐Baseline + ☐FU1/☐ FU2/ ☐FU3	
		☐Mons Pubis ☐Labia	☐Baseline + ☐FU1/☐ FU2/ ☐FU3	
		☐Mons Pubis ☐Labia	$\square$ Baseline + $\square$ FU1/ $\square$ FU2/ $\square$ FU3	
		☐ Mons Pubis ☐ Labia	$\square$ Baseline + $\square$ FU1/ $\square$ FU2/ $\square$ FU3	
		☐ Mons Pubis ☐ Labia	$\square$ Baseline + $\square$ FU1/ $\square$ FU2/ $\square$ FU3	
		☐Mons Pubis ☐Labia	$\square$ Baseline + $\square$ FU1/ $\square$ FU2/ $\square$ FU3	
		☐Mons Pubis ☐Labia	$\square$ Baseline + $\square$ FU1/ $\square$ FU2/ $\square$ FU3	
		☐Mons Pubis ☐Labia	$\square$ Baseline + $\square$ FU1/ $\square$ FU2/ $\square$ FU3	
		☐Mons Pubis ☐Labia	$\square$ Baseline + $\square$ FU1/ $\square$ FU2/ $\square$ FU3	
		☐Mons Pubis ☐Labia	$\square$ Baseline + $\square$ FU1/ $\square$ FU2/ $\square$ FU3	
		☐Mons Pubis ☐Labia	$\square$ Baseline + $\square$ FU1/ $\square$ FU2/ $\square$ FU3	
		☐Mons Pubis ☐Labia	$\square$ Baseline + $\square$ FU1/ $\square$ FU2/ $\square$ FU3	
		☐Mons Pubis ☐Labia	☐Baseline + ☐FU1/☐ FU2/ ☐FU3	
		☐Mons Pubis ☐Labia	$\square$ Baseline + $\square$ FU1/ $\square$ FU2/ $\square$ FU3	
		☐Mons Pubis ☐Labia	☐Baseline + ☐FU1/☐ FU2/ ☐FU3	

Confidential 23

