## 3 Study Objectives

## 3.1 Primary Objectives

- To evaluate the safety of treating the mons pubis, labia and vaginal introitus with the Freeze Diamondpolar applicator.
- To evaluate the safety of the internal treatment of the vagina with the investigational applicator.
- To verify the efficacy of using the Freeze Diamondpolar applicator for improving general skin appearance of the Mons pubis and Labia including improvement of skin irregularities and skin laxity of the female genitalia and introitus.
- To determine and/or quantify any potential regenerative properties associated with the study treatments.

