#### 7.2.2 Skin improvement assessment

The assessment of general improvement in skin appearance will be accomplished by an independent evaluation of photographs.

At baseline and in FU3, a photograph of each of the treated areas will be taken per the photography guidelines. A copy of the images will be sent to independent reviewers. The reviewers will evaluate, for each time point, the improvement in skin appearance in comparison to base line based on the GAI scale (See Appendix B). The results of the evaluation will be recorded in the Photographs assessment log (see appendix

Confidential 10

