### 8 Study Analysis Plan

## 8.1 Study Hypothesis

The study will confirm that the Freeze Diamond Polar applicator is safe for the treatment of the mons pubis, vaginal introitus and labia, and will result in improvement in skin laxity and skin irregularities.

The study will also confirm that the investigational applicator is safe for internal treatment of the vagina.

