### 8.2 Sample Size Justification

The proposed study is a feasibility study for evaluating the safety and the efficacy of using the Freeze Diamond Polar applicator for treatment of the mons pubis, vaginal introitus and labia anatomical areas and the investigational applicator for treatment of the vagina. Based on previous experience with other RF devices, we believe that the proposed study sample of 10 subjects per each anatomical area (total of 10) will be sufficient to evaluate the safety and the efficacy of the treatment and to obtain qualitative assessments of comfort levels experienced during treatments.

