## 12.4 Appendix D - Histopathology Molecular Assay Assessment log

## Principal Investigator's Form

Subject ID (initials)	Treated Area	Slide Set #	Assay Result
	☐ Mons Pubis ☐ Labia ☐ Introitus	$\square$ Baseline + $\square$ FU1/ $\square$ FU2/ $\square$ FU3	
	☐ Mons Pubis ☐ Labia ☐ Introitus	$\square$ Baseline + $\square$ FU1/ $\square$ FU2/ $\square$ FU3	
	☐ Mons Pubis ☐ Labia ☐ Introitus	$\square$ Baseline + $\square$ FU1/ $\square$ FU2/ $\square$ FU3	
	☐ Mons Pubis ☐ Labia ☐ Introitus	$\square$ Baseline + $\square$ FU1/ $\square$ FU2/ $\square$ FU3	
	☐ Mons Pubis ☐ Labia ☐ Introitus	$\square$ Baseline + $\square$ FU1/ $\square$ FU2/ $\square$ FU3	
	☐ Mons Pubis ☐ Labia ☐ Introitus	$\square$ Baseline + $\square$ FU1/ $\square$ FU2/ $\square$ FU3	
	☐ Mons Pubis ☐ Labia ☐ Introitus	$\square$ Baseline + $\square$ FU1/ $\square$ FU2/ $\square$ FU3	
	☐ Mons Pubis ☐ Labia ☐ Introitus	$\square$ Baseline + $\square$ FU1/ $\square$ FU2/ $\square$ FU3	
	☐ Mons Pubis ☐ Labia ☐ Introitus	$\square$ Baseline + $\square$ FU1/ $\square$ FU2/ $\square$ FU3	
	☐ Mons Pubis ☐ Labia ☐ Introitus	$\square$ Baseline + $\square$ FU1/ $\square$ FU2/ $\square$ FU3	
	☐ Mons Pubis ☐ Labia ☐ Introitus	$\square$ Baseline + $\square$ FU1/ $\square$ FU2/ $\square$ FU3	
	☐ Mons Pubis ☐ Labia ☐ Introitus	$\square$ Baseline + $\square$ FU1/ $\square$ FU2/ $\square$ FU3	
	☐ Mons Pubis ☐ Labia ☐ Introitus	$\square$ Baseline + $\square$ FU1/ $\square$ FU2/ $\square$ FU3	
	☐ Mons Pubis ☐ Labia ☐ Introitus	$\square$ Baseline + $\square$ FU1/ $\square$ FU2/ $\square$ FU3	
	☐ Mons Pubis ☐ Labia ☐ Introitus	$\square$ Baseline + $\square$ FU1/ $\square$ FU2/ $\square$ FU3	
	☐ Mons Pubis ☐ Labia ☐ Introitus	$\square$ Baseline + $\square$ FU1/ $\square$ FU2/ $\square$ FU3	
	☐ Mons Pubis ☐ Labia ☐ Introitus	$\square$ Baseline + $\square$ FU1/ $\square$ FU2/ $\square$ FU3	
	☐ Mons Pubis ☐ Labia ☐ Introitus	$\square$ Baseline + $\square$ FU1/ $\square$ FU2/ $\square$ FU3	
	☐ Mons Pubis ☐ Labia ☐ Introitus	☐Baseline + ☐FU1/☐ FU2/ ☐FU3	
	☐ Mons Pubis ☐ Labia ☐ Introitus	☐ Baseline + ☐ FU1/☐ FU2/ ☐ FU3	

Confidential 24

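### Appendices E, C and F, as supplied, do not collect all that the text calls for: no pain score for the internal treatment, no introitus GAI score, no response type

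*Combined protocol and SAP*

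**What the plan says.** **Treatment.** Section 2 gives each subject three treatments with both applicators. Section 7.5 specifies external treatment of the mons pubis, labia and introitus with one applicator, and internal treatment of the vagina with a second.

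**Objectives and sample size.** The efficacy objective in Section 3.1 extends to "skin irregularities and skin laxity of the female genitalia and introitus". A separate primary objective is "To evaluate the safety of the internal treatment of the vagina with the investigational applicator". Section 8.1 expects the external applicator to be "safe for the treatment of the mons pubis, vaginal introitus and labia, and will result in improvement in skin laxity and skin irregularities". Section 8.2 lists "treatment of the mons pubis, vaginal introitus and labia anatomical areas and the investigational applicator for treatment of the vagina" and holds that "the proposed study sample of 10 subjects per each anatomical area (total of 10) will be sufficient to evaluate the safety and the efficacy".

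**Photographs.** Under Section 7.2.2, at baseline and FU3, "a photograph of each of the treated areas will be taken per the photography guidelines". Independent reviewers grade these on the GAI scale and the result goes in the photographs log. Every row of that log (Appendix C) offers "Mons Pubis ☐Labia". The histopathology log (Appendix D) offers "Mons Pubis ☐ Labia ☐ Introitus".

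**Pain.** Section 4.2 makes the VAS a secondary endpoint after each of the three treatments. Step 9 of Section 7.5, which follows the external and internal steps, asks for it immediately after each treatment. Appendix E is headed for the mons pubis and labia procedures and has one line for each.

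**Response.** Section 4.3 and the synopsis define the investigator-assessed response by its type, its intensity and the time it takes to resolve. Section 7.2.1 gives erythema, edema and purpura as examples. Appendix F has one 1–5 score immediately after treatment and one at about 30 minutes.

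**The concern.** A form that lacks a field loses the data whatever the text intends, and the three losses differ in kind.

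- **Appendix E.** A secondary endpoint would have no value for the investigational applicator. Pain immediately after treatment cannot be scored again later.
- **Appendix C.** One named area of the primary efficacy objective has no place for its score. This is the least serious loss, because the photographs can be graded later if they were taken.
- **Appendix F.** A score of 3 could mean moderate erythema, edema or purpura. The endpoint as defined could not be reported from this form, and the type cannot be reconstructed afterwards.

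**Working it through.** The plan gives no figure for these forms beyond 10 subjects per area, so the check compares fields and then counts.

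| Form | What the text calls for | What the form shows |
|---|---|---|
| Appendix E | VAS after each treatment; each treatment uses both applicators (2, 4.2, 7.5) | Lines for mons pubis and labia; none for the internal treatment |
| Appendix C | GAI grading of each treated area; introitus named as an area (3.1, 7.2.2, 8.1, 8.2) | Mons pubis and labia; no introitus |
| Appendix F | Type and intensity (4.3, synopsis, 7.2.1) | Intensity at two time points; no type |

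Inputs: 10 subjects (8.2), 3 sessions (2), 2 response time points (Appendix F), and 1 FU3-versus-baseline comparison (4.1). All subjects are assumed to complete.

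- **Internal VAS:** 10 × 3 = 30 scores due. The form has 0 lines, so 0 of 30. The two existing lines yield 10 × 3 × 2 = 60 marks, all external.
- **Introitus GAI, per evaluator:** 10 × 1 = 10 scores due. The form has 0 boxes, so 0 of 10. Over three external areas 10 × 3 = 30 scores are due and the form provides for 10 × 2 = 20, so one third has no box.
- **Response scores:** 10 × 3 × 2 = 60, of which 0 carry a type. After treatment 1 there are 10 × 2 = 20, and 20/60 = 33%. These 20 contribute to the interim safety report in Section 8.3, which is used to adjust later treatment parameters.

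The number of evaluators is not stated, so GAI counts are per evaluator. The counts show how much goes unrecorded; they do not measure the effect on any conclusion.

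**The case against.** **The CRF may hold these fields.** It is not supplied, and the copy of Appendix F may be cut: its visit line shows only Tx1. This stands and limits confidence on Appendix F, although its two score lists look complete. For Appendix E it carries less weight, because the form's footer has its scores transcribed to the final CRF.

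**The introitus may be counted with the labia.** Section 5.1 mentions only the mons pubis and labia. But Sections 7.5 and 8.2 name the introitus separately, and Appendix D gives it its own box.

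**Each treatment may mean each session.** On that reading too, a form limited to two external areas leaves internal pain unrecorded. Section 8.2 promises only qualitative comfort assessments, and Appendix H asks which applicator was most comfortable and what was felt. Neither item is a VAS score.

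**Adverse events are recorded.** Much of this stands. Sections 9.1 to 9.1.2 and 9.1.6 capture the nature, severity and device or procedure relatedness of reactions logged as AEs, including pain, purpura, edema and burns. But 9.1.2 does not separate the two applicators, and Section 7.5 calls transient erythema and edema the normal response, so these may not be logged.

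**Stronger readings.** A reader might infer that the text requires site and applicator on Appendix F. It does not: step 8 of Section 7.5 asks for one examination after both treatments, and the need for site follows only from the separate safety objectives. Nor can one say that internal safety goes unassessed, since AEs, vaginal pH and biopsies are collected. A reader might also infer that the IRB's review of the first 10 subjects is compromised, but Appendix I does not say which data that review uses.

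**Conclusion.** The point holds for the forms as supplied and should be fixed. Appendix E omits the internal treatment (0 of 30 VAS scores) and Appendix C omits the introitus (0 of 10 GAI scores per evaluator); confidence in both is high. Appendix F omits response type (60 untyped scores), with moderate confidence. All counts assume 10 completing subjects and no equivalent field in the unseen CRF.

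The consequence is incomplete endpoint data, with the pain scores and response types beyond recovery. The analysis is descriptive, and the interim report is qualitative, also draws on AEs and does not affect continuation, so no formal test or stopping decision is at stake.

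**What to change.** **To match the text:**

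1. Appendix E: add a line for the internal treatment. Cost: one mark per session, 10 × 3 = 30 at 10 subjects.
2. Appendix C: add an introitus option. Cost: 10 more GAI scores per evaluator.
3. Appendix F: add a response-type field (erythema, edema, purpura, other).
4. Section 8.3: report the results by area.

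**Recommended, though the text does not require it:** on Appendix F, also record the site of each response seen at the examination already planned in step 8. Each applicator has its own primary safety objective, and reactions after treatment 1 inform later parameters. Table 1 describes this tool as an examination of skin, so state whether the vaginal wall is part of it. Do not add an internal examination for this purpose.

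**Alternatives.** If these data will not be collected, narrow the objectives, the response endpoint and the hypothesis to what the forms cover. If the CRF already has the fields, cite it in Section 7.2 and align the appendices.

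The overall cost is revised forms with IRB approval under Section 10.9 and some extra recording at existing visits.

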## 12.4 Appendix D - Histopathology Molecular Assay Assessment log

## Principal Investigator's Form

Subject ID (initials)	Treated Area	Slide Set #	Assay Result
	☐ Mons Pubis ☐ Labia ☐ Introitus	$\square$ Baseline + $\square$ FU1/ $\square$ FU2/ $\square$ FU3	
	☐ Mons Pubis ☐ Labia ☐ Introitus	$\square$ Baseline + $\square$ FU1/ $\square$ FU2/ $\square$ FU3	
	☐ Mons Pubis ☐ Labia ☐ Introitus	$\square$ Baseline + $\square$ FU1/ $\square$ FU2/ $\square$ FU3	
	☐ Mons Pubis ☐ Labia ☐ Introitus	$\square$ Baseline + $\square$ FU1/ $\square$ FU2/ $\square$ FU3	
	☐ Mons Pubis ☐ Labia ☐ Introitus	$\square$ Baseline + $\square$ FU1/ $\square$ FU2/ $\square$ FU3	
	☐ Mons Pubis ☐ Labia ☐ Introitus	$\square$ Baseline + $\square$ FU1/ $\square$ FU2/ $\square$ FU3	
	☐ Mons Pubis ☐ Labia ☐ Introitus	$\square$ Baseline + $\square$ FU1/ $\square$ FU2/ $\square$ FU3	
	☐ Mons Pubis ☐ Labia ☐ Introitus	$\square$ Baseline + $\square$ FU1/ $\square$ FU2/ $\square$ FU3	
	☐ Mons Pubis ☐ Labia ☐ Introitus	$\square$ Baseline + $\square$ FU1/ $\square$ FU2/ $\square$ FU3	
	☐ Mons Pubis ☐ Labia ☐ Introitus	$\square$ Baseline + $\square$ FU1/ $\square$ FU2/ $\square$ FU3	
	☐ Mons Pubis ☐ Labia ☐ Introitus	$\square$ Baseline + $\square$ FU1/ $\square$ FU2/ $\square$ FU3	
	☐ Mons Pubis ☐ Labia ☐ Introitus	$\square$ Baseline + $\square$ FU1/ $\square$ FU2/ $\square$ FU3	
	☐ Mons Pubis ☐ Labia ☐ Introitus	$\square$ Baseline + $\square$ FU1/ $\square$ FU2/ $\square$ FU3	
	☐ Mons Pubis ☐ Labia ☐ Introitus	$\square$ Baseline + $\square$ FU1/ $\square$ FU2/ $\square$ FU3	
	☐ Mons Pubis ☐ Labia ☐ Introitus	$\square$ Baseline + $\square$ FU1/ $\square$ FU2/ $\square$ FU3	
	☐ Mons Pubis ☐ Labia ☐ Introitus	$\square$ Baseline + $\square$ FU1/ $\square$ FU2/ $\square$ FU3	
	☐ Mons Pubis ☐ Labia ☐ Introitus	$\square$ Baseline + $\square$ FU1/ $\square$ FU2/ $\square$ FU3	
	☐ Mons Pubis ☐ Labia ☐ Introitus	$\square$ Baseline + $\square$ FU1/ $\square$ FU2/ $\square$ FU3	
	☐ Mons Pubis ☐ Labia ☐ Introitus	☐Baseline + ☐FU1/☐ FU2/ ☐FU3	
	☐ Mons Pubis ☐ Labia ☐ Introitus	☐ Baseline + ☐ FU1/☐ FU2/ ☐ FU3	

Confidential 24

## 12.5 Appendix E - VAS (Visual Analog Scale)

Check one of the following boxes to indicate tod	day's Treatment Visit:	
Tx1 □ Tx2□ Tx3□		
Immediate Pain Assessment for the Venus Freez	e (MP)  Mons Pubis and Labia procedures:	
Pain assessment of Mons Pubis Please make a mark on the line below to indicato were administered the treatment:	e how much discomfort or pain you experienced when yo	эu
No Pain	Pain as bad as it can be	
Pain assessment of Labia		
Please make a mark on the line below to indicate were administered the treatment:	e how much discomfort or pain you experienced when you	ou
No Pain	Pain as bad as it can be	
Subject Initials/ID Number:		
Date (mm/dd/yy):		
Study Personnel Transcribing V.A.S. Assessment	Scores to Final CRF:	

Confidential 25

Protocol: CS2815v4 Approval Number: IRCM- Approval Date:
Continuing Review Date: February 24, 2017

## 12.6 Appendix F - Investigator Immediate and Short Term Response

Check one of the following boxes to indicate today's Treatment Visit:
Tx1
Circle one of the scores below that best presents the IMMEDIATE tissue response to the treatment
1=none
2=trace
3=moderate
4=marked
5=severe
Circle one of the scores below that best presents the SHORT TERM (~30mins post treatment) tissue response
to the treatment
1=none
2=trace
3=moderate
4=marked
5=severe

Confidential 26

## 12.7 Appendix G – Subject Duration of Post Treatment Adverse Events Questionnaire

Check one of the following boxes to indicate today's Treatment/Follow up Visit:  Tx2  Tx3 FU3.							
Please check the box that correlates with the duration of possible post treatment side effects by checking the box that corresponds to the day your symptoms resolved:							
	Day of the Treatment	1 day after	2 day after	3 day after	4 day after	7 day after	
Redness							
Swelling							
Crusting							
Blistering							

Confidential 27

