## 7 Study Procedures

### 7.1 Study duration and timelines

Each subject will be enrolled and scheduled for three treatments at approximately four week intervals and return for a follow-up visit at one month (± seven days) after the last treatment for evaluation of the treated areas. During each visit various tasks will be performed as detailed in the study flow chart (Appendix A).

Each subject will therefore participate in the study for a period of at least 3 months. The study is anticipated to be completed within six months.

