#### 7.2.1 Post Treatment Responses

Immediate and short term responses (erythema, edema, purpura, etc.) will be assessed by the investigator immediately and up to 30 min post treatment, by a 5 level scale: 1=none; 2=trace; 3=moderate; 4=marked; 5=severe.

In addition, subject reporting on duration of post-treatment adverse events questionnaire will be collected after each treatment and at the follow-up visit.

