## 7.2.4.2 Level of improvement and satisfaction

Subject's Improvement and Satisfaction with treatment will be recorded by using the GAI scale at the last follow up visit (see Appendix B).

Table 1 - Clinical Evaluation Tools

Claim/task	When to conduct?	Tool		
Photography	Baseline, immediately before	Standardized digital photographs		
	treatments 2, 3, FU 3			
Vaginal pH	Baseline, immediately before	Standard pH paper		
	treatments 2, 3, FU 3			
Histopathology & Molecular	Baseline, immediately before	Histology slides, special staining		
Studies	treatments 2, 3, FU 3	and assays.		
Immediate and short term	Immediately following treatments	Examination of skin in the treated		
response evaluation by	1-3	area based on 5 level scale		
investigator		(Appendix F)		
Subject's duration of post-	Before treatments 2, 3, FU 3	Subject Questionnaire on post		
treatment adverse events questionnaire		treatment response (Appendix G)		
Subjects discomfort/pain	Immediately following treatments	VAS (Appendix E)		
assessment	1-3			
Subjects improvement/	FU3.	GAI (see Appendix B)		
satisfaction assessment				
score				
Independent reviewers score	At the end of the study	GAI (see Appendix B)		

Confidential 11

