#### 9.1.6 Anticipated Outcome Related Adverse Events

Anticipated adverse events in this study include pain, tenderness, purpura, persistent erythema, edema, burn, blistering, crusting, hyperpigmentation, hypopigmentation, scarring and potential for damage to hair follicles within the treatment area and subsequent loss of hair within the treatment area.

Any anticipated AE that occurs at any time during or after the use of the study device must be recorded by the Investigator. If the anticipated AE, in the opinion of the Investigator, is likely to affect the safety of the subjects or the conduct of the study, the ethic committee will be notified of the effect within 10 working days. In this study if an adverse event occurs the Investigator will continue following the subject until the case is resolved or up to 1 month following the last visit, whichever comes first.

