## 9.3 Risk/ Benefit Analysis

#### 9.3.1 Risks

The potential risks for adverse effects of the treatment procedure include but are not limited to mainly to transient edema or erythema in the treated area the following events were also identified as low probability anticipated adverse effects: pain, tenderness, erythema lasting longer than 6 hours, mild to moderate edema lasting more than 6 hours, burn, blistering, crusting, hyperpigmentation, hypopigmentation, scarring, potential damage to hair follicles and loss of hair within the treatment zones and eye irritation. (See Appendix I for Additional Safety Background).

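### Appendix G has no visible box for a reaction that never occurred, outlasted day 7 or is still present, so duration summaries from this form are truncated and biased downward

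*Combined protocol and SAP*

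**What the plan says.** Appendix G lists four symptoms (redness, swelling, crusting, blistering) and asks the subject to give the duration of each "by checking the box that corresponds to the day your symptoms resolved". The first column is "Day of the Treatment"; the others are 1, 2, 3, 4 and 7 days after. The form carries visit check boxes for Tx2, Tx3 and FU3.

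On timing, section 7.2.1 states "subject reporting on duration of post-treatment adverse events questionnaire will be collected after each treatment and at the follow-up visit". Table 1 gives "Before treatments 2, 3, FU 3". Section 7.1 sets "three treatments at approximately four week intervals and return for a follow-up visit at one month (± seven days) after the last" treatment. Each form therefore looks back about four weeks.

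Section 4.3 includes, in the first safety endpoint, the time a response takes to subside. The investigator's scale (section 7.2.1, Appendix F) ends at about 30 minutes. Section 8.3 promises descriptive statistics and an adverse event listing. It does not mention blank rows on Appendix G.

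Separately, section 9.1 requires adverse events to be recorded on the CRF with onset and resolution dates, section 9.1.6 requires every anticipated event to be recorded, and Appendix A marks adverse event recording at all four visits.

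**The concern.** A form that asks only for the day of resolution needs a way to say that nothing happened and a way to say that it has not resolved. Neither is visible here, and the scale stops at day 7 although the subject is answering at about day 28. The reactions of most interest for safety, those that do not clear quickly, are the ones the form cannot place.

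This matters because safety is a primary objective for both applicators (section 3.1) and because duration is named in the endpoint. Appendix I also says that the IRB will review safety results from the first 10 patients before an expanded study of up to 300 is submitted. A duration table built from this form would look more reassuring than the experience behind it if any reaction ran past day 7.

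**Working it through.** The plan states no figure on this point, so there is nothing to reproduce. The check is a count of what the form can record.

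**1. Days with a box.** Boxes exist for days 0, 1, 2, 3, 4 and 7, which is 6 days. Taking the interval as 28 days (section 7.1, Appendix A), days 0 to 28 are 29 days. Days without a box: 29 − 6 = 23, made up of days 5 and 6 (2) and days 8 to 28 (21). With the ± 7 day window around FU3, and one month taken as 28 days, the look-back is 21 to 35 days. The days after day 7 without a box are then 21 − 7 = 14 to 35 − 7 = 28.

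**2. What each course of a symptom produces on the form.**

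| True course | Form completed literally | If the subject improvises |
|---|---|---|
| Never occurred | Blank | Treatment day ticked |
| Resolved on day 0–4 or 7 | Correct box | Correct box |
| Resolved on day 5 or 6 | Blank | Day 4 or day 7 |
| Resolved on day 8 or later | Blank | Day 7 |
| Still present at the visit | Blank | Day 7 |

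**3. Direction of the error past day 7.** Section 8.3 gives no rule for blanks, so there are three possibilities. If blanks are dropped, the longest durations leave the summary. If blanks are read as no reaction, the longest reactions count as none. If day 7 is ticked, duration is capped at 7. All three understate duration. For days 5 and 6 the error can go either way and is at most 2 days for a ticked box (day 5 entered as 7, or day 6 entered as 4).

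**4. Other sources of duration in days.** Appendix F stops at about 30 minutes and has no field for time to resolution. The VAS is taken immediately after treatment. Appendix H does not ask how long a reaction lasted. That leaves the adverse event record, which has dates but is a free-standing record and is nowhere linked to Appendix G.

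**5. Illustration.** The documents give no rate of reactions lasting past day 7. Assume 2 of 10 subjects have one and complete the form literally. The exact (Clopper-Pearson) 95% limits for x of n are the 0.025 quantile of Beta(x, n − x + 1) and the 0.975 quantile of Beta(x + 1, n − x), with lower limit 0 when x = 0.

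- Truth, 2/10: 2.5% to 55.6%.
- Form with blanks read as none, 0/10: upper limit 1 − 0.025^(1/10) = 30.8%, so 0% to 30.8%.
- If the truth were 1/10: 0.3% to 44.5%.

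**6. Visit schedule.** Appendix A marks this questionnaire at Visit 1 as well as Visits 2 to 4. Table 1 and the form's own check boxes have only Tx2, Tx3 and FU3.

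**The case against.** The best argument against the point is the adverse event record. Section 9.1 covers anything the patient reports or the physician observes, with onset and resolution dates. Section 9.1.6 makes recording of anticipated events mandatory and follows them until resolution or up to one month after the last visit. Appendix I adds its own reporting and long-term follow-up for burns and device complications. A reader might infer that Appendix G is the study's only source of duration data and that persistent events would go unseen. The documents do not support that: redness, pigment change or scarring at day 28 has a dated route outside this form. What survives is narrower. Nothing requires the form and the adverse event record to be reconciled, and a blank row gives staff no cue to ask.

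A second tempting inference is that safety information is lost because the form covers few of the anticipated events. Section 9.1.6 lists "pain, tenderness, purpura, persistent erythema, edema, burn, blistering, crusting, hyperpigmentation, hypopigmentation, scarring and potential for damage to hair follicles" with hair loss, 12 types if follicle damage and hair loss are one item. The form has rows for 4 (33%), or 4 of 13 (31%) if they are split. That count describes the form and does not measure harm. Sections 7.5 and 7.6.1 describe transient erythema and edema as the usual response, and the form fits those. Scarring, pigmentation and hair loss are better found on examination and entered as adverse events. Even so, section 9.3.1 foresees "erythema lasting longer than 6 hours, mild to moderate edema lasting more than 6 hours, burn, blistering, crusting", and section 9.1.6 foresees erythema that persists. The redness row exists but has no way to say so.

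Third, section 4.3 describes the response as assessed by the investigator, so Appendix G is not expressly the source for time to subside. That is fair, but the investigator's form has no field for it, and no other structured form measures in days.

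Fourth, the table text has one unlabelled cell at the end of each row, just after day 7. Empty trailing cells occur in other tables too, so this is probably an artefact of reading the file, but the original page must be checked.

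**Conclusion.** The point holds as a defect of this form. As labelled, 23 of 29 days in a 28-day look-back have no box, and no reaction, late resolution and continuing reaction can all leave the same blank row. Duration summaries drawn from it are truncated at day 7 and understate duration whenever a reaction lasts longer. How often that happens is unknown. If no reaction outlasts day 7, that bias does not arise and only the unclear blanks and the gap at days 5 and 6 remain. It would also be wrong to say that every completed form is in error: all share the layout, but only rows with a late or continuing reaction, a day 5 or 6 resolution, or an unexplained blank are affected.

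The conclusion assumes that the unlabelled last column is not a longer-duration option, and that Appendix G will be used to describe time to subside. This is a cheap improvement in a descriptive feasibility study with a parallel dated adverse event record.

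**What to change.** 1. Check the original page of Appendix G for a label on the last column.
2. Add the options *Did not occur*, *5 days*, *6 days*, *After day 7 (day __)* and *Still present today*, so that every row has exactly one answer and a blank means missing.
3. State that any reaction marked as after day 7 or still present is entered in the adverse event record with its dates.
4. In section 8.3, summarise occurrence first, then duration among those affected, with *Still present today* treated as censored at the visit date. Report blank rows as missing.
5. Separately, reconcile the Visit 1 mark in Appendix A with Table 1 and the form's check boxes.

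Rows for the other anticipated events are optional. The cost is one revised page, a short addition to section 8.3 and slightly longer completion at each visit. Treatments and the visit schedule do not change. The change is best made before forms are collected, because blanks already returned could not be reliably reinterpreted.
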